APPENDIX 1. SAMPLE SIZE JUSTIFICATION

The data used for the sample size calculations came from 2 sources:

- a. Data for alglucosidase alfa came from the LOTS extension (NCT00455195) which is a long-term extension study in which subjects were treated with the standard of care ERT (alglucosidase alfa) for up to 9 years; and
- b. Data for ATB200/AT2221 came from Amicus' ongoing single-arm study, ATB200-02, which enrolled 4 cohorts of subjects. Of these, 2 cohorts had relevant data for use in the sample size calculations: Cohort 1 – ambulatory subjects who had been on ERT treatment for 2 to < 7 years; and Cohort 3 – ambulatory subjects who had not been previously treated with ERT (ie, ERT-naïve).

Firstly, effect sizes were estimated using % predicted 6MWD data from ATB200-02 Cohort 1 subjects (n = 10) treated with alglucosidase alfa for 2 to 6 years before switching to ATB200/AT2221, ATB200-02 Cohort 3 subjects (n = 5) who were ERT-naïve before starting ATB200/AT2221, and from a LOTS extension study (n = 22) where subjects were treated with alglucosidase alfa for up to 9 years ([van der Ploeg, Clemens et al. 2017](#)). Longitudinal percent predicted 6MWD data were extracted from Figure 5 of [van der Ploeg, Clemens et al. 2017](#) and subjects were 1:1 matched to ATB200-02 subjects on the basis of treatment duration and baseline % predicted 6MWD. A treatment duration window was specified for each ATB200-02 subject extending from the time of switching from alglucosidase alfa to ATB200/AT2221 (eg, 4.4 years) to the end of the 9 or 12-month treatment period with ATB200/AT2221 (eg, 5.4 years). In order to be eligible for matching to a given ATB200-02 subject, a LOTS extension study subject had to have at least one 6MWD value within the corresponding treatment duration window and one 6MWD value before and after the window. The LOTS extension subjects were then sequentially matched to ATB200-02 subjects based on having the smallest difference in baseline % predicted 6MWD at the corresponding treatment duration starting point. Once the LOTS extension subject with the closest baseline 6MWD was matched to a given ATB200-02 subject, that subject was removed from the pool and the remaining subjects were matched. Calculation of the slope of change in % predicted 6MWD for each matched LOTS extension subject was then based upon cubic spline values extracted every 3 months across the corresponding 9 or 12-month treatment duration window \pm 6 months on each side.

Based on this analysis, ATB200-02 Cohort 1 subjects switching from alglucosidase alfa to ATB200/AT2221 had a mean 12-month slope of change of +5.87% predicted 6MWD compared to a mean 12-month slope of -2.15% for matched subjects in the LOTS extension remaining on alglucosidase alfa. The mean difference between groups was +8.01%, favoring ATB2200/AT2221 with a standard deviation of +8.49%. For the ATB200-02 Cohort 3 subjects who were ERT-naïve before starting on ATB200/AT2221, the mean 12-month slope of change was +12.61% predicted 6MWD compared to a mean 12-month slope of -0.65% for matched subjects in the LOTS extension remaining on alglucosidase alfa. The mean difference between groups was +13.26%, favoring ATB2200/AT2221 with a standard deviation of +2.85%. Thus, the effect size of ATB200/AT2221 in ERT-naïve subjects was larger than the effect size in ERT-switch subjects.

Secondly, when the subjects in ATB200-02 Cohort 1 (ERT-switch subjects) were combined with Cohort 3 (ERT-naïve subjects) into a single LOPD sample (n = 15), the overall mean 12-month slope of change for subjects receiving ATB200/AT2221 in ATB200-02 was +8.11% predicted

6MWD compared to a mean 12-month slope of -1.65% for the matched subjects in the LOTS extension on alglucosidase alfa. The mean difference between groups was +9.76% favoring ATB2200/AT2221 with a standard deviation of +7.43%. The resulting estimated standardized effect size (mean difference divided by standard deviation of difference) is then 1.31 (95% CI: 0.60, 2.00) for subjects switching from alglucosidase alfa to ATB200/AT2221.

Thirdly, the sample size calculation used a conservative standardized effect size of 0.7 for the inter-group analysis in the combined ERT-switch and ERT-naïve population. This reduction from the estimated 1.31 effect size was intended to help account for uncertainty of the effect size estimate due to the relatively small sample size, potential selection bias in ATB200-02 versus LOTS study extension data, other potential biases in period effects in combining ERT-switch and ERT-naïve subjects, as well as imbalance in known and unknown risk factors, outliers, informative missing data, and dropout patterns. The standard effect size of 0.7, which is close to the lower confidence limit, constitutes about one-half of the originally calculated standardized effect size of 1.31, thus making it quite conservative. Of note, the standard effect size of 0.7 corresponds to a % predicted 6MWD of 5.0. In the range of expected subject age, weight, and height (using [Enright and Sherrill 1998](#) for % predicted 6MWD calculation), a % predicted value of 5.0 equates to a measured 6MWD value of between 20 to 40 meters. Such a 6MWD range is within the minimal clinically important difference in 6MWD for adults with pathology, and it may also be clinically important across multiple subject groups ([Bohannon and Crouch 2017](#)). In addition, 20 to 40 meters is within the range of group-level 6MWD differences (investigational treatment versus comparator) that served as the basis for regulatory approval.

APPENDIX 2. DESCRIPTIONS OF EFFICACY ENDPOINTS

1. 6MWD: The 6-minute walk distance, measured in meters (m), is the distance walked on the 6MWT.

2. Percent predicted 6MWD is calculated as:

$$\% \text{ predicted 6MWD} = (\text{actual 6MWD} / \text{predicted 6MWD}) * 100,$$

(rounded up or down based on standard rounding rules), where the predicted values are derived for males and females using the following [Enright and Sherill 1998](#) equations:

Males: $6\text{MWD} = (7.57 \times \text{Height in cm}) - (5.02 \times \text{Age in years}) - (1.76 \times \text{Weight in kg}) - 309 \text{ m};$

Females: $6\text{MWD} = (2.11 \times \text{Height in cm}) - (5.78 \times \text{Age in years}) - (2.29 \times \text{Weight in kg}) + 667 \text{ m}.$

3. Pulmonary function tests (PFTs):

- Sitting forced vital capacity (FVC): FVC (L) and percent predicted FVC (%)
- Supine forced vital capacity: FVC (L) and percent predicted FVC (%)
- Maximum inspiratory pressure (MIP): MIP (cm of water [cm H₂O]) and % predicted MIP (%)
- Maximum expiratory pressure (MEP): MEP (cm of water [cm H₂O]) and % predicted MEP (%)
- SNIP (cm of water [cm H₂O]) and % predicted SNIP (%)

The percent predicted values of MIP, MEP, and SNIP will be calculated as:

$$\% \text{ predicted} = (\text{actual result} / \text{predicted result}) * 100,$$

where the predicted results are obtained using the reference equations in Table 12. The equations for MIP and MEP are from [Uldry and Fitting 1995](#); the equation for SNIP is from [Evans and Whitelaw 2009](#).

Table 12: Predicted Equations for MIP, MEP, and SNIP

PFT	Male	Female
MIP	120 – (0.41 x Age in years)	108 – (0.61 x Age in years)
MEP	174 – (0.83 x Age in years)	131 – (0.86 x Age in years)
SNIP	126.8 – (0.42 x Age in years)	94.9 – (0.22 x Age in years)

4. Manual muscle testing (MMT):

- Right/left shoulder adduction
- Right/left shoulder abduction
- Right/left elbow flexion

- Right/left elbow extension
- Right/left hip flexion
- Right/left hip abduction
- Right/left knee flexion
- Right/left knee extension

Each manual muscle test is evaluated on a scoring scale from 0 to 5, as follows: 0 = no muscle movement; 1 = visible muscle movement, but no movement at the joint; 2 = movement at the joint, but not against gravity; 3 = movement against gravity, but not against added resistance; 4 = movement against resistance, but less than normal; 5 = normal strength.

- MMT Lower Extremity score: The total score for MMT lower extremity strength is obtained by summing the test scores across the following 8 body parts: right/left hip flexion, right/left hip abduction, right/left knee flexion, and right/left knee extension. The total score ranges from 0 to 40, with lower scores indicating lower muscle strength. That is, Lower = Hip scores + Knee scores.
 - MMT Upper Extremity score: The total score for MMT upper extremity strength is obtained by summing the test scores across the following 8 body parts: right/left shoulder abduction, right/left shoulder adduction, right/left elbow extension, and right/left elbow flexion. The total score ranges from 0 to 40, with lower scores indicating lower muscle strength. That is, Upper = Shoulder scores + Elbow scores.
 - MMT Total score: The MMT total score is the sum of the lower extremity score and the upper extremity score. The total score ranges from 0 to 80, with lower scores indicating lower overall muscle strength. That is, Total = Upper extremity + Lower extremity.
 - Proximal body muscle groups include right/left hip flexion, right/left hip abduction, right/left shoulder abduction, and right/left shoulder adduction with the total score ranging from 0 to 40, based on these 8 muscle groups. That is, Proximal = Shoulder scores + Hip scores.
5. Quantitative muscle test (QMT) was measured using the hand-held dynamometer (HHD). Larger values/scores (in kg) indicate greater muscle strength.
- Right/left shoulder adduction
 - Right/left shoulder abduction
 - Right/left elbow flexion
 - Right/left elbow extension
 - Right/left hip flexion
 - Right/left hip adduction
 - Right/left hip abduction

- Right/left knee flexion
 - Right/left knee extension
 - QMT value for upper extremities (kg) is obtained by summing up the values/scores from the following: right/left shoulder abduction, right/left shoulder adduction, right/left elbow extension, and right/left elbow flexion.
 - QMT value for lower extremities (kg) is obtained by summing up the values/scores from the following: right/left hip flexion, right/left hip abduction, right/left hip adduction, right/left knee flexion, and right/left knee extension.
 - QMT total value (kg) is obtained by adding up the QMT upper extremity and QMT lower extremity values/scores.

- Gowers' maneuver score (based on the subject lying down on the floor, then rising from the floor to get to a standing position). This is scored as: 1 = normal; 2 = butt first maneuver, one hand on floor; 3 = butt first maneuver, two hands on floor; 4 = unilateral hand support on thigh; 5 = bilateral hand support on thighs; 6 = arises only with aid of an object (table, chair, cane, etc); 7 = unable to rise.
- Chair score (based on the subject arising from a sitting position in a chair to a standing position). This is scored as: 1 = normal; 2 = with wide base and/or difficulty but without support; 3 = with support on one thigh; 4 = with support on both thighs; 5 = with support on arms of chair or on a table; 6 = not possible.

For each of the above motor function tests, the actual time (in seconds [s]) that the subject takes to perform the test is also recorded for analysis.

The total GSGC score ranges from 4 (normal performance) to 27 (worst performance).

8. Timed Up and Go [TUG] test represents the time it takes the subject to stand up from the chair, walk to the line on the floor (about 3 meters), turn around, walk back to the chair, and sit down, all at the regular pace.
9. R-PAct Scale total score: The Rasch-built Pompe-specific Activity (R-PAct) scale consists of 18 questions, each scored on a scale from 0 to 2 as follows: 0 = no; 1 = yes, but with difficulty; 2 = yes, without difficulty.

The total score is calculated simply by summing up the observed scores across the 18 items and it ranges from 0 to 36, with higher values representing lower level of disease impact on the muscles.

10. EQ-5D-5L: European Quality of Life-5 Dimensions 5 Response Levels health status:

The EQ-5D-5L consists of the EQ-5D descriptive system and the EQ-VAS (visual analogue scale). Each of the 5 dimensions (mobility, self-care, usual activities, pain/discomfort, and anxiety/depression) has 5 categorical responses/levels of perceived problems coded as follows:

Level 1 = indicating no problem; Level 2 = indicating slight problems;
Level 3 = indicating moderate problems; Level 4 = indicating severe problems;
Level 5 = indicating extreme problems (for pain and anxiety) or indicating unable to (for mobility, self-care, and activity).

The EQ-VAS is a quantitative measure of health outcome that reflects the patient's own judgement. The EQ-5D is a 5-digit number (a categorical variable) that describes the subject's health state.

11. SGIC: The Subject's Global Impression of Change consists of the following 8 items (or functional areas):

- overall physical wellbeing
- effort of breathing
- muscle strength
- muscle function
- ability to move around
- activities of daily living
- energy level
- level of muscular pain

Each of the 8 functional items is scored on a 7-point rating scale that ranges from '1 = very much worse' to '7 = very much improved.'

For each functional item, a tertiary response variable (improving, declining, stable) will be defined as: "Improving" which consists of improved, moderately improved, and very much improved; "Declining" consists of worse, moderately worse, and very much worse; and "Stable" equals no change.

12. PGIC: The Physician's Global Impression of Change is based on a single item that is scored on a 7-point rating scale. The response options/category are similar to the SGIC described above.

APPENDIX 3. SAMPLE SAS PROGRAMS

All analysis programs will be submitted. Three sample SAS codes are provided below to illustrate the MMRM analysis (based on ITT-OBS), ANCOVA (based on ITT-LOCF) and the composite endpoint analysis that combines two separate logistic regression analyses.

Sample Code for the MMRM Analysis

```
/******  
/** Description: Sample program for implementing the MMRM Analysis. */  
/** This sample program applies to the primary analysis of the primary */  
/** endpoint(6MWD), and can be adapted to all other MMRM analyses */  
/** specified in the SAP. */  
/* */  
/* Response variable(CHG): Change from baseline at each visit timepoint*/  
/** Explanatory variables in the model are: */  
/** TRTPN AVISIT TRTPN*AVISIT SEX BASE ERTEXP AGEBL HGTBL WGTBL */  
/* */  
/* Assume that the 6MWD dataset is called ANADAT */  
/* */  
/* Some Definitions: */  
/** TRTPN = Treatment group (1 = new treatment, 2 = control) */  
/** AVISIT = Analysis Visit */  
/** ERTSTA = ERT status (Experienced or Naïve) */  
/******  
  
/******  
/* Perform the analysis. Then obtain treatment means and differences at */  
/* each visit, with p-values and CIs. */  
/******  
  
ods output LSMeans=lsm LSMEstimate=lsmest;  
proc mixed data = anadat method = reml;  
class TRTPN AVISIT ERTSTA SEX USUBJID;  
model CHG = TRTPN AVISIT TRTPN*AVISIT SEX BASE ERTSTA AGEBL HGTBL WGTBL /  
ddfm=kr;  
repeated AVISIT / type=UN subject=USUBJID;  
lsmeans TRTPN*AVISIT / slice=AVISIT alpha=0.05 OM diff cl s; *** Obtain  
treatment means and differences at each visit, with CIs.**;  
  
lsmestimate TRTPN*AVISIT "Treat vs. Control at Week 52" 0 0 0 1 0 0 0 -1  
/ upper testvalue=0; *** Get treatment diff and 1-sided p-value **;  
  
lsmestimate TRTPN*AVISIT `Treat vs. Control at Week 52' 0 0 0 1 0 0 0 -1 /  
testvalue=0 alpha=0.05 cl; **Get treatment diff and 2-sided p-value *;
```

Sample Code for the ANCOVA

```
/******  
/* ANCOVA is based on the ITT-LOCF population. This sample program can */  
/* be adapted to other ANCOVA analyses for the 6MWD, percent predicted */  
/* FVC, and all others specified in the SAP. */  
/******  
  
/* Perform the ANCOVA, obtain estimates of the treatment means, treatment */  
/* differences, p-values and 95% CIs. */  
  
ods output LSMeans=lsm LSMEstimate=lsmest;  
proc mixed data = anadat;  
  class TRTPN ERTSTA SEX;  
  model CHG = TRTPN SEX BASE ERTSTA AGEBL HGTBL WGTBL /ddfm=kr;  
  lsmeans TRTPN / OM s alpha=0.05 cl diff; ** Obtain lsmeans and lsmean  
differences;  
  
  lsmestimate TRTPN "Treat vs. Control at Week 52" 1 -1 / upper  
  testvalue=0; **Get treatment diff and 1-sided p-value at W52 *;  
  
  lsmestimate TRTPN `Treat vs. Control at Week 52' 1 -1 / testvalue=0  
  alpha=0.05 cl; **Get treatment diff, 2-sided p-value, 95% CIs at W52*;
```

Sample Code for the Analysis of Composite Endpoint

```
*****  
* Implement separate logistic analyses for positive responses and *  
* negative responses, and then combine the two results using weights. *  
*  
* Assume input dataset (COMPOS) is structured as below, and has the *  
* following variables: RESPONSE, TRTPN, ERTSTA, DUR, SEX, AGEBL *  
*  
  1 1 N 2.4 F 0  
  3 1 N 3.5 M 0  
  1 1 E 2.7 M 37  
  0 2 N 5.6 F 0  
  3 1 E 7.0 M 67  
  3 2 N 2.0 F 0  
  2 1 E 4.1 M 64  
  1 2 N 4.8 M 0  
  0 2 E 7.7 F 28  
  3 1 E 5.5 F 32  
  2 2 E 6.3 F 48  
  . . . . .  
  
* RESPONSE variable = composite response with values 0, 1, 2, 3 *  
* TRTPN = Treatment group (1 = new treatment, 2 = control) *  
* ERTSTA = ERT status (Experienced or Naïve) *  
* DUR = duration of ERT: value for ERT-experienced, and 0 for naïve.*  
*****;  
  
** Analysis of positive responses vs. not positive responses **;
```

```
data comp1;
  set compos;
  if response=3 then resp1='Y';
  else resp1='N';
run;

** Analysis of stable responses vs. negative responses;
data comp2;
  set compos;
  if response=3 then delete;
  if response=2 then resp2='Y';
  else resp2='N';
run;

** Run two separate logistic regression models **;
ods output ParameterEstimates=test1;
proc genmod data=comp1;
  class TRTPN ERTSTA SEX;
  model resp1(event='Y') = TRTPN ERTSTA DUR SEX AGEBL / dist=binomial
                        link=logit type3;
run;

ods output ParameterEstimates=test2;
proc genmod data=comp2;
  class trt ert;
  model resp2(event='Y') = TRTPN ERTSTA DUR SEX AGEBL / dist=binomial
                        link=logit type3;
run;

data combo;
  merge test1(where=(level1='1') keep=level1 estimate stderr
              rename=(estimate=estimate1 stderr=stderr1))
        test2(where=(level1='1') keep=level1 estimate stderr
              rename=(estimate=estimate2 stderr=stderr2));
run;

** Calculate the weights, combine the test statistics and obtain the **;
** p-value using weight as the inverse of the standard error estimate **;
data combo2;
  set combo;
  w1=1/stderr1**2;
  w2=1/stderr2**2;
  z1=estimate1/stderr1;
  z2=estimate2/stderr2;
  zw=(w1/(w1+w2)*z1 + w2/(w1+w2)*z2)/sqrt((w1/(w1+w2))**2+(w2/(w1+w2))**2);
  pvalue=1-cdf('normal',zw);
run;
```

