4.3. Sample Size and Power Considerations

The primary endpoint for this study is the change from baseline to Week 52 in the 6MWD.

Using a 2-group t-test with a 1-sided significance level of 0.025 and a 2:1 randomization ratio, a total of 99 subjects (66 subjects in the ATB200/AT2221 group and 33 subjects in the alglucosidase alfa/placebo group) would yield approximately 90% power to detect a clinically meaningful standardized effect size of 0.7 between the 2 groups in a superiority test for the primary endpoint. This calculation was performed using nQuery 8[®].

Assuming a 10% dropout rate (after randomization), a total of approximately 110 subjects were planned to be randomized to ensure 99 evaluable patients.

Details of the sample size justification are described in [Appendix 1](#).

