8.7. Composite Subject-level Response Analysis

As a supplementary analysis to the primary and key secondary endpoints for the study, and to support the interpretation of further clinical benefit, an analysis using a composite subject-level response will be performed based on a multi-domain responder index (MDRI). This MDRI will be defined to capture the totality of evidence using the 3 relevant clinical outcomes, 6MWD, FVC (% predicted), and MMT lower extremity score. The MDRI approach provides a framework for presenting the totality of data combining the 3 components which measure motor function, pulmonary function, and muscle strength, which are the domains that are impacted in individuals with LOPD. A clinically meaningful threshold for within-subject changes in each clinical outcome and the categorization of each outcome are provided in Table 8.

Table 8: Threshold for Defining Clinically Meaningful Within-subject Change

Clinical Outcome	Declining	Stable	Improving
6MWD ^a	< -6%	-6% to < +6%	\geq +6%
% predicted FVC ^b	< -3%	-3% to < +3%	\geq +3%
MMT lower extremity score ^a	< -7%	-7% to < +7%	\geq +7%

^a Threshold is based on the percentage change from baseline.

^b Threshold is based on the change from baseline.

The above thresholds are consistent with published MCID (minimal clinically important differences) values for comparable instruments in similar disease populations (Schrover, Evans et al. 2017; du Bois, Weycker et al. 2011; Baschung Pfister, de Bruin et al. 2018).

The ordinal composite response across all 3 ternary outcomes is defined as follows:

- 3 = significant improvement: subject is either improving on all 3 outcomes, or is improving on both 6MWD and % predicted FVC;
- 2 = moderate improvement: subject is improving on either 6MWD only, or % predicted FVC only, or both 6MWD and MMT lower extremity, or both % predicted FVC and MMT lower extremity;
- 1 = minor: subject is improving on MMT lower extremity score only;

- 0 = no improvement: subject is not improving on any of the 3 clinical outcomes.

The main interest for this analysis is the inter-group comparison. There is no intra-subject comparison for the MDRI approach.

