This method defines a hierarchical ordinal categorical response variable, for which a continuation logit model (Agresti 2002) will be used to perform separate logistical regression analyses adjusting for baseline risk factors including ERT status (ERT-naïve or ERT-experienced), duration of prior alglucosidase alfa (only for ERT-experienced subjects), gender, and baseline age.

The results of these separate logistic regression analyses are then pooled to test the overall null hypothesis that treatment with ATB200/AT2221 is less effective than alglucosidase alfa/placebo with respect to either the positive composite response (ie, significant improvement) or the negative response (ie, minor/no improvement). The inter-group comparison will be based on the combined analysis of comparisons of the positive response rates of significant improvements and the negative response rates of minor/no improvement.

Additional details regarding the separate logistic regression analyses and test against the overall null hypothesis are described below.

The “significant improvement” response category is considered as positive response, the “moderate improvement” category is considered as stable response, and “minor/no improvement” is considered as negative response. Treatment (ie ATB200/AT2221) is expected to have high positive responses and low negative responses, while the control (ie, alglucosidase alfa/placebo) is expected to have high negative responses and low positive responses). Separate logistic regression models are used to analyze and test (1) positive responses vs. not positive responses (where “not positive responses” includes the “moderate improvement” and “minor/no improvement” categories; (2) negative responses vs. stable responses, conditional on subjects who are not positive responders.

The respective hypotheses for Test 1 and Test 2 are stated as follows: $H_{10}: \delta_1 \leq 0$ vs. $H_{1A}: \delta_1 > 0$ and $H_{20}: \delta_2 \leq 0$ vs. $H_{2A}: \delta_2 > 0$, where δ_1 and δ_2 are the effect sizes for comparing treatment to control for Test 1 and Test 2 respectively.

Let the logistic regression model for Test 1 be:

$$\text{logit}(p_{1,Positive}) = \ln \frac{p_{1,Positive}}{p_{1,Not pos}} = \beta_{1,0} + \beta_{1,1} \text{TRT} + \beta_{1,2} \text{ERT} + \beta_{1,3} \text{DUR} + \beta_{1,4} \text{SEX} + \beta_{1,5} \text{AGE}$$

and Test 2 be:

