$$\text{logit}(p_{2,Negative}) = \ln \frac{p_{2,Neg}}{p_{2,Stable}} = \beta_{2,0} + \beta_{2,1} \text{TRT} + \beta_{2,2} \text{ERT} + \beta_{2,3} \text{DUR} + \beta_{2,4} \text{SEX} + \beta_{2,5} \text{AGE}$$

For any coefficient β , the Wald statistic is given by $Wald = b/se_b$, where b is the estimate for β and se_b is the standard error for β , and the Wald statistic is approximately normally distributed. Therefore, in testing the null hypothesis about the treatment effect, say $\beta_{1,2} = 0$ (for Test 1), the test statistic for treatment effect is: $(b_{1,2} - 0)/se_b = b_{1,2}/se_b$.

Let $Z_1 = b_1/se_{b_1}$ and $Z_{2/1} = b_{2/1}/se_{b_{2/1}}$ be the test statistics for testing treatment effect in Test 1 and Test 2 respectively, where Z_1 and $Z_{2/1}$ are standardized to have standard normal distributions (so that each has mean = 0 and variance = 1).

The inter-group comparison is based on the combined analysis of the positive response rates of significant improvements and the negative response rates of minor/no improvement. The overall null and alternative hypothesis ($H_0: H_{10} \cap H_{20}$) is tested against the alternative hypothesis ($H_A: H_{1A} \cup H_{2A}$) based on the combination test statistic:

$$Z = \frac{w_1}{w_1+w_2} Z_1 + \frac{w_2}{w_1+w_2} Z_{2/1}, \text{ where } w_1 \text{ and } w_2 \text{ are weights (constants) for the random}$$

variables Z_1 and $Z_{2/1}$ respectively (Rpatel 2019). The weights, w_i , represent the information fraction in test i . The expected value of Z is given by:

$$E(Z) = \frac{w_1}{w_1+w_2} E(Z_1) + \frac{w_2}{w_1+w_2} E(Z_{2/1}) = 0, \text{ under } H_0.$$

Assuming independence of Z_1 and $Z_{2/1}$, the variance of Z is given as:

$$\begin{aligned} Var(Z) &= \left(\frac{w_1}{w_1+w_2}\right)^2 Var(Z_1) + \left(\frac{w_2}{w_1+w_2}\right)^2 Var(Z_{2/1}) \\ &= \left(\frac{w_1}{w_1+w_2}\right)^2 + \left(\frac{w_2}{w_1+w_2}\right)^2 \end{aligned}$$

Inference is based on the standardized score Z_w , where

$$Z_w = \frac{\frac{w_1}{w_1+w_2} Z_1 + \frac{w_2}{w_1+w_2} Z_{2/1}}{\left[\left(\frac{w_1}{w_1+w_2}\right)^2 + \left(\frac{w_2}{w_1+w_2}\right)^2\right]^{1/2}}$$

follows the standard normal distribution under the null hypothesis. A 1-sided p-value for testing against the overall null hypothesis H_0 is given by $p = 1 - \Phi(z_w)$, where $\Phi(\cdot)$ is the cumulative distribution function of a random variable that follows the standard normal distribution.

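### The SAP does not give one workable specification of the supplementary MDRI combination test: weight, Test 2 code, coefficient label and Test 2 direction each conflict

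*SAP*

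**What the plan says.** The MDRI classifies each subject from 6MWD, % predicted FVC and the MMT lower extremity score. Section 8.7 introduces it "As a supplementary analysis to the primary and key secondary endpoints for the study". Test 1 compares positive with not-positive responders. Test 2 compares negative with stable responders among those who are not positive. The two Wald statistics, Z1 and Z2/1, are combined with weights w1 and w2 and standardized, and the result is "A 1-sided p-value for testing against the overall null hypothesis".

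Four elements of the specification appear in more than one form.

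- **Weight.** Section 8.7 says that the weights "represent the information fraction in test" i, and gives no formula. The Appendix 3 comment speaks of a "p-value using weight as the inverse of the standard error estimate". The code sets `w1=1/stderr1**2`, and w2 likewise.
- **Treatment coefficient.** In the Section 8.7 models the first slope (beta1,1) belongs to TRT and the second (beta1,2) to ERT. The Wald paragraph then reads "in testing the null hypothesis about the treatment effect, say" beta1,2 = 0.
- **Test 2 code.** Appendix 3 lists the dataset variables as RESPONSE, TRTPN, ERTSTA, DUR, SEX and AGEBL. The Test 1 step has TRTPN, ERTSTA and SEX in its CLASS statement. The Test 2 step has `trt` and `ert` instead, although its model uses the same terms as Test 1.
- **Direction of Test 2.** Section 8.7 models the log odds of a negative against a stable response, sets the alternative as delta2 > 0 and adds Z2/1. The code makes the stable response the event.

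**The concern.** Protocol Section 15.3.2.3.1 uses this composite to support the interpretation of clinical benefit, and leaves the intergroup comparison and the overall test to the SAP. SAP Section 2 says that the SAP supersedes the protocol, and Appendix 3 says that all analysis programs will be submitted. The MDRI p-value should therefore be fixed by the SAP alone.

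It is not. Two statisticians who follow different lines would report different p-values, and the sample program cannot settle the matter because its Test 2 step fails. If the weight or the direction is chosen after unblinding, the choice can be influenced by the result.

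**Working it through.** **Inputs.** The documents give no MDRI response rates, standard errors, power or p-value, so there is no figure of the plan's own to reproduce. All SEs, Zs, response rates and odds ratios (ORs) below are assumptions. The simulations use the group sizes in SAP Section 4.3 ("66 subjects in the ATB200/AT2221 group and 33 subjects in the alglucosidase alfa/placebo group"). Section 8.7 sets no alpha for the MDRI, so 1-sided 0.025 is assumed, as elsewhere in the SAP.

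**1. Does the weight change the p-value?** After standardization, Zw = (w1·Z1 + w2·Z2) / √(w1² + w2²). Take SE1 = 0.7, SE2 = 0.5, Z1 = 2.2, Z2 = 1.0.

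- w = 1/SE: weights 1.429 and 2. Zw = (3.143 + 2)/√(2.041 + 4) = 5.143/2.458 = 2.09, p = 0.018.
- w = 1/SE²: weights 2.041 and 4. Zw = (4.490 + 4)/√(4.165 + 16) = 8.490/4.491 = 1.89, p = 0.029.

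Other assumed values:

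| SE1, SE2 | Z1, Z2 | p with 1/SE | p with 1/SE² |
|---|---|---|---|
| 1.0, 0.5 | 2.2, 1.0 | 0.030 | 0.066 |
| 0.80, 0.45 | 2.2, 1.2 | 0.0168 | 0.0353 |
| 0.80, 0.45 | 1.2, 2.2 | 0.0061 | 0.0070 |

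In simulation (200,000 trials per scenario, unadjusted Wald log ORs, control positive rate 10–25%, 35–50% of control non-positives stable), the two weights disagreed on significance in about 3–9% of trials with an effect and in under 1% under the null.

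**2. Which weight is more efficient?** The quantities combined are Z statistics, already divided by their SEs. Under a common log OR, E(Zi) is proportional to 1/SEi and the best weight on Z is 1/SE. With r the ratio of the SEs, 1/SE² keeps the fraction (1 + r³)/√((1 + r²)(1 + r⁴)) of the noncentrality:

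- r = 1.5: 0.986
- r = 2: 9/√(5 × 17) = 0.976
- minimum: 0.975, at r = 2.3

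At that minimum, 80% power becomes 78.0% and 90% becomes 88.5%. With both ORs at 2.7, the simulated loss was 1.3 to 3.3 points. With unequal ORs, 1/SE² ranged from a loss of 8.7 points (45.3% to 36.6%; ORs 4 and 1.5, control positive rate 10%) to a gain of about 3 points (76.9% to 79.9%; ORs 1.5 and 4, control positive rate 10%).

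**3. Is type I error affected?** Simulated values were 0.016 to 0.020 for both weights, below 0.025.

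**4. Does the Test 2 code run?** The final step selects Test 1 with "merge test1(where=(level1='1') keep=level1 estimate stderr", and Test 2 in the same way. In Test 1 the level 1 row is TRTPN = 1, because ERTSTA is coded N/E and SEX is coded F/M. In Test 2, `trt` and `ert` are not in the described dataset, and the text variables ERTSTA and SEX enter the model unclassed. TRTPN is unclassed too, so there is no level 1 row for the merge. Neither z2 nor the combined p-value can be computed.

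**5. What does the direction conflict do?** Modelling negative against stable reverses the sign of the coefficient obtained by modelling stable against negative. In the first example, entering Z2/1 = −1.0 for the same benefit gives (4.490 − 4)/4.491 = 0.11, p = 0.46 with 1/SE², and (3.143 − 2)/2.458 = 0.46, p = 0.32 with 1/SE. With both ORs at 2.7 and the 1/SE² weight, simulated power falls from 68–79% to 0.02–4.5% if the written Test 2 coefficient is used as it stands.

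**The case against.** The strongest reply is that the SAP text and the executable code agree on the weight. Section 8.7 divides each weight by their sum and calls it an information fraction. With w = 1/SE², that ratio is exactly each test's share of the total information. Only the comment is out of line, and correcting it is enough. This stands, and it is why the fix leaves the choice of weight open.

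The subscript is clerical. The sentence names the treatment effect and the code extracts the TRTPN row, so a reader who infers that ERT status would be tested goes beyond the documents. The CLASS error sits in code offered as a sample and fails visibly, so it cannot silently produce a rival p-value. Both points stand. Even so, Appendix 3 is the only place where the weight is given a formula, so its comment and code need to agree and to run.

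Two stronger readings are tempting. One is that the coded weight loses power. That holds under a common log OR, where the loss is small. Section 8.7 does not assume a common OR, and with unequal effects 1/SE² can do better. The other is that Test 1 is the less precise test, so that significant improvement gets too little weight. No document gives the rates needed to say so. With both ORs at 2.7, the simulated median SEs were 0.67 (Test 1) and 0.48 (Test 2) at a control positive rate of 10% with 35% of control non-positives stable. At 25% they were 0.48 and 0.55, and the order reverses.

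**Conclusion.** The inconsistencies are certain and can be read directly from Section 8.7 and Appendix 3. The MDRI p-value has two incompatible weight descriptions, a mislabelled coefficient, a Test 2 direction that differs between text and code, and a sample program that cannot return the combined result. The weight conflict can move p across 0.025. Taken literally, the direction conflict has the larger effect.

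The consequence for the trial is limited. The MDRI is supplementary and lies outside the family-wise error control of Section 8.4. Neither weight inflates type I error, and efficiency does not decide between them. Every numerical size given here rests on assumed rates, ORs and SEs, and the simulations omit the covariates. The correction should be made, but it does not touch the primary or key secondary conclusions.

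**What to change.** Before database lock:

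1. State one weight formula in Section 8.7 and use it in the text, the comment and the code. Either set w = 1/SE in the code and describe the weights as the square root of each test's information, or keep 1/SE² and correct the comment. The first is efficient under a common log OR. The second is acceptable if it is what was intended.
2. Change beta1,2 to beta1,1 in the Wald statement, with the matching estimate.
3. Change the Test 2 statement to `class TRTPN ERTSTA SEX;`.
4. Align Test 2. The simplest route is to write the Section 8.7 model as stable against negative, which matches the code, delta2 > 0 and the plus sign on Z2/1.

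The cost is a few line edits in the SAP, with no change to data collection or sample size. A run on dummy data would confirm that both treatment rows reach the final step.
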